An adverse event may be any unfavourable and unintended change (including a deviation of a laboratory indicator from the norm), symptom or disease, the time of occurrence of which does not exclude a causal relationship with the use of the medicinal product, regardless of the presence or absence of a relationship with the use of the medicinal product. The parameters of an AE will be assessed in relation to the variables: severity (non-serious, serious AE), foreseeability (foreseen, unforeseen), severity (mild, moderate, severe, life-threatening, fatal), causality (no/yes; if yes: definite, probable, possible, doubtful, conditional, unclassifiable) and outcome (progression to SAE, stabilisation of condition, recovery without consequences, recovery with consequences, improvement in condition, unknown) as follows:

Serious adverse events (SAEs)

For the purposes of this protocol and in accordance with the legal requirements (National

Standard of the Russian Federation "Good Clinical Practice" GOST R52379-2005 dated 25.09.2005), a serious adverse medical event will be considered to be any adverse medical event that, regardless of the dose of the medicinal product, has resulted in death, is life-threatening, requires hospitalisation or its prolongation hospitalization or its prolongation, has resulted in permanent or significant disability or incapacity for work, is a congenital anomaly or birth defect or other medically significant event.

Severity of AEs

The investigator assesses the severity of an adverse event according to the Common Terminology Criteria for Adverse Events (CTCAE) current version at the time of the trial. If an adverse event cannot be classified according to the CTCAE criteria, the Investigator will select the closest description of the severity of the adverse event from those given in the classification based on personal clinical experience:

Severity	Severity	Definition/Description
1	Mild	No symptoms or mild symptoms, only clinical or diagnostic follow-up is required; no intervention is indicated
2	Moderate	Only minimal, localised or non-invasive interventions are indicated; limitation of daily living activities
3	Severe	Severe or clinically significant but not immediately life-threatening; hospitalization or prolongation of hospitalization indicated; disability; limitation of self-care in activities of daily living
4	Life-threatening/ Disability to work	Life-threatening consequences, urgent intervention required

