5	Fatal	Death associated with an adverse event

Determination of the relationship of AE to the investigational product:

The investigator should assess the association of the adverse event with the investigational product:

No - clearly and unequivocally related to extraneous causes only, and does not meet the criteria for an unclassifiable, conditional, doubtful, possible, probable or certain relationship.

Yes - there is a reliable temporal relationship with the use of the investigational product.

Criteria:

- may have been caused by a clinical condition or external factors or other prescribed treatments;
- clear temporal relationship between discontinuation of the investigational product or dose reduction and improvement;
- resumes upon rechallenge;
- is consistent with the known nature of the response to the investigational product.

The degree of certainty of causality with the investigational product will be assessed using the WHO scale, taking into account the trial design (multiple administration):

Definite. Clinical manifestations of AEs, abnormalities of laboratory parameters occur during the period of IP administration, cannot be explained by the presence of existing diseases and the influence of other factors.

Probable. Clinical manifestations of AEs, abnormalities of laboratory parameters are related in time to the use of the investigational product, unlikely to be related to concomitant diseases or other factors.

Possible. Clinical manifestations of AEs, changes in laboratory parameters are related in time to the IP intake, but they can be explained by the presence of concomitant diseases or

taking other drugs and the influence of chemical compounds.

Doubtful. Clinical manifestations of AEs, changes in laboratory parameters occur in the absence of a clear temporal relationship with the use of the investigational product; there are other factors (drugs, diseases, chemicals) that may be the cause of their occurrence.

Conditional. Clinical manifestations of an AE, abnormalities of laboratory parameters attributed to an AE are difficult to assess. Additional data is needed for evaluation, or the data is currently being analysed.

Unclassifiable. Reports of suspected AE cannot be evaluated because there is insufficient information or it is contradictory.

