Foreseeability: assessed only for AEs treated as an adverse reaction. An unexpected adverse reaction is an adverse reaction, the nature, severity or outcome of which does not correspond to the information in the current instructions for medical use of the medicinal product or in the investigator's leaflet for an unregistered medicinal product.

Outcome:

The outcome of an AE is assessed as follows:

Transition to the SAE:	AE resulted in a condition that meets the criteria of seriousness (resulted in death, was life-threatening, required hospitalization of the patient or its prolongation, resulted in permanent or pronounced disability or incapacity, congenital anomalies or malformations, required medical intervention to prevent the development of these conditions. In case of any unexpected suspected transmission of an infectious agent through a medicinal product has occurred)
Stabilization of the condition (no change in condition):	AE has not resolved
Recovery with consequences	The resolution of the AE has occurred, but the patient still has some residual effects
Recovery/termination of an AE without consequences:	The AE has completely resolved without observed residual events
Improved condition:	Decrease in the severity of an AE
Unknown:	The outcome of an AE is unknown because the patient did not show up for the follow-up examination and attempts to obtain follow-up information were unsuccessful (lost for follow-up)

Terms used in relation to a medicinal product:

An adverse *reaction* is an unintentional adverse reaction of the body associated with the use of a medicinal product/ investigational product, suggesting at least a possible relationship with the use of the suspected medicinal product/ investigational product.

Unexpected adverse reaction - an adverse reaction, the nature, severity or outcome of which does not correspond to the information in the current instructions for medical use of the medicinal product or in the investigator's leaflet for an unregistered medicinal product.

A serious unexpected adverse reaction (SUAR) is an unexpected adverse reaction that is characterized by features of a SAE.

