**Plan for statistical analysis of efficacy and safety parameters**

Table 21. Analysing the distribution of AEs by severity (template)

Severity		Investigational Product	
		Mexitol®	Placebo
Mild	Abs.		
	%		
Moderate	Abs.		
	%		
Severe	Abs.		
	%		
Life-threatening/ Disability to work	Abs.		
	%		
Fatal	Abs.		
	%		
Inter-group differences		Pearson 's χ^2 criterion or Fisher's exact test	p-value

Table 22. Relationship of AEs to investigational product (template)

The association of the adverse event with the investigational drug		Investigational Product	
		Mexitol®	Placebo
Yes	Abs.		
	%		
No	Abs.		
	%		
Differences between preparations		Pearson 's χ^2 criterion or Fisher's exact test	p-value

Table 23: Analysis of the distribution of AEs by administration of the Investigational Product (template)

Relationship to Investigational Product administration		Investigational Product	
		Mexitol®	Placebo
Definite.	Abs.		
	%		
Probable.	Abs.		
	%		
Possible.	Abs.		
	%		
Doubtful.	Abs.		

Version 1.0 of 12.11.2021

Protocol-Specific Version for Protocol #PHS-APIS-004-MEX-SOL-TAV. version 1.3 dated 07.06.2021

CONFIDENTIAL

page 51 of 58

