**Plan for statistical analysis of efficacy and safety parameters**

	%		
Conditional.	Abs.		
	%		
Unclassifiable.	Abs.		
	%		
Inter-group differences	Pearson 's χ^2 criterion or Fisher's exact test		p-value

Table 24. Analysis of the distribution of AEs by foreseeability (template)

Expectancy	Investigational Product		
	Mexitol®	Placebo	
Expected	Abs.		
	%		
Unexpected	Abs.		
	%		
Inter-group differences	Pearson 's χ^2 criterion or Fisher's exact test		p-value

Table 25. Analysis of AR distribution (template)

AE	Investigational Product		
	Mexitol®	Placebo	
AR	Abs.		
	%		
Not an AR	Abs.		
	%		
Inter-group differences	Pearson 's χ^2 criterion or Fisher's exact test		p-value

Table 26. Analysis of the distribution of AEs by seriousness (template)

Seriousness	Investigational Product		
	Mexitol®	Placebo	
Serious	Abs.		
	%		
Nonserious	Abs.		
	%		
Inter-group differences	Pearson 's χ^2 criterion or Fisher's exact test		p-value

Table 27. Analysing the distribution of AEs by actions taken (template)

Version 1.0 of 12.11.2021

Protocol-Specific Version for Protocol #PHS-
APIS-004-MEX-SOL-TAV. version 1.3 dated
07.06.2021

CONFIDENTIAL

page 52 of 58

Plan for statistical analysis of efficacy and safety parameters

Actions taken	Investigational Product	
	Mexidol®	Placebo
No action was taken	Abs.	
	%	
Other (specific actions taken will be indicated)	Abs.	
	%	
Inter-group differences	Pearson 's χ^2 criterion or Fisher's exact test	p-value

Table 28. Analysis of the distribution of AEs by outcome (template)

Outcome	Investigational Product	
	Mexidol®	Placebo
Transition to SAE	Abs.	
	%	
Stabilization of the condition (no change in condition):	Abs.	
	%	
Recovery with consequences	Abs.	
	%	
Recovery/termination of an AE without consequences:	Abs.	
	%	
Improved condition	Abs.	
	%	
Unknown:	Abs.	
	%	
Inter-group differences	Pearson 's χ^2 criterion or Fisher's exact test	p-value

Plan for statistical analysis of efficacy and safety parameters

Table 29. Summary table of the incidence of reported AEs in the group taking Mexidol by severity with randomization numbers of patients (N=) (template)

AE/code, PT according to MedDRA version	Mild AE		Medium AE		Moderate AE		Life-threatening AE		Fatal AE		Total		Total
	R	UR	R	UR	R	UR	R	UR	R	UR	R	UR	R+UR

Table 30. Summary table of the incidence of reported AEs in the group taking placebo by severity with randomization numbers of patients (N=) (template)

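### The causality coding forces doubtful, conditional and unclassifiable events into the related (Yes) row of SAP Table 22, contradicting the definition of Yes or the adverse-reaction threshold

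*Protocol*

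**What the plan says.** Protocol section 8.3 sets up causality in two levels: "causality (no/yes; if yes: definite, probable, possible, doubtful, conditional, unclassifiable". The text on determining the relationship then defines the answers. For *Yes* it says: "Yes - there is a reliable temporal relationship with the use of the investigational product". *No* is reserved for an event due only to outside causes that "does not meet the criteria for an unclassifiable, conditional, doubtful, possible, probable or certain relationship". *Doubtful* covers events that "occur in the absence of a clear temporal relationship with the use of the investigational product" and for which another possible cause exists. *Conditional* means that more data are needed or are being analysed. *Unclassifiable* means that the information is insufficient or contradictory. SAP section 10 repeats these definitions almost unchanged.

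Later in section 8.3 an adverse reaction is defined as "suggesting at least a possible relationship with the use of the suspected medicinal product", and a serious unexpected adverse reaction (SUAR) is built on that term. SAP section 10 uses the same threshold.

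The SAP templates use these categories in several ways:

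- "Table 22. Relationship of AEs to investigational product (template") has rows for *Yes* and *No*, with a between-arm test.
- Table 23 lists all six grades by arm.
- "Table 25. Analysis of AR distribution (template") splits events into adverse reaction or not, again with a between-arm test.
- Tables 29, 30, 34 and 35 have R and UR columns, which the SAP's abbreviation list does not explain.

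**The concern.** A site following the rule literally has no consistent answer for a doubtful event: *No* is closed to it, and *Yes* asserts a link in time that the grade itself denies. Two planned between-arm tests would then classify the same events by different thresholds, both readable as relatedness, with no text to tell the reader why they differ.

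The second trial objective is a comparative evaluation of adverse events, so a related-event table with an unclear cut-off is a real weakness. Putting events with little or no evidence of a link into the related row of both arms also makes that row a poorer measure of drug-related events. If the mapping is settled only after unblinding, the choice is open to challenge.

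**Working it through.** No figure in the plan needs reproducing. The check sets each grade against the four rules that apply to it: the nesting, the definition of *Yes* and the definition of *No* (Protocol 8.3; definitions repeated in SAP section 10), and the adverse-reaction threshold (Protocol 8.3; SAP section 10).

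| Grade | Coded under | Fits the definition of *Yes*? | May be coded *No*? | Adverse reaction? |
|---|---|---|---|---|
| Definite | Yes | no conflict | no | yes |
| Probable | Yes | no conflict | no | yes |
| Possible | Yes | no conflict | no | yes |
| Doubtful | Yes | contradicts it | no | no |
| Conditional | Yes | not established | no | not established |
| Unclassifiable | Yes | not established | no | not established |

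The table shows two separate faults. Only *doubtful* contradicts the definition of *Yes* outright. *Conditional* and *unclassifiable* say nothing about timing; their fault is that they count as *Yes* without establishing at least a possible relationship.

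For either arm, let n be the number of events in a grade:

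- Table 22 *Yes* = n(definite) + n(probable) + n(possible) + n(doubtful) + n(conditional) + n(unclassifiable)
- Table 25 adverse reactions, if that table follows the stated definition = n(definite) + n(probable) + n(possible)
- Difference = n(doubtful) + n(conditional) + n(unclassifiable)

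The difference is zero if no event falls in these three grades and positive otherwise, so against the at-least-possible threshold the error can only overstate. Neither document gives counts or expected shares by grade, so it has no computable size.

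For Tables 29, 30, 34 and 35 the check ends sooner. Neither document says whether R follows the *Yes*/*No* coding or the adverse-reaction definition, so those columns could be filled either way.

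**The case against.** The strongest reply is that the information is not lost. Table 23 reports every grade by arm with its own test, so any split can be rebuilt. Table 25 applies the adverse-reaction threshold, and the adverse-reaction and SUAR definitions agree with each other. Two tables that cut the same events differently are not in themselves an error. The safety conclusion (Protocol 8.1) rests on all AEs, and Protocol 9.7.3 compares the number of patients with AEs, as SAP Table 20 does with a relative risk; neither comparison uses causality. All of this stands and limits the point to Table 22, the R/UR tables and the missing rule. It does not remove the contradiction in the coding instruction.

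Some stronger readings are tempting but not supported:

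- *Most events after a stroke will be doubtful.* Under Protocol 8.3, an event related in time but explicable by another disease is *possible*, not doubtful. AEs are recorded from the first dose through 70 days of treatment, so many such events would be *possible*, which raises no conflict.
- *The gap can be sized from EPICA.* Protocol 2.3.2 reports 41 events, 3 of them possibly related (3/41 = 7.3%), and most with no association. If 30% to 70% of the remaining 92.7% were doubtful, Table 22 would show 7.3% + 0.30 × 92.7% = 35% to 7.3% + 0.70 × 92.7% = 72% as related. That share has no source, EPICA's causality scale is not described, and its investigators mostly chose absence of a link.
- *Serious events awaiting data will go unreported.* Protocol 8.3.2 sends every SAE to the sponsor or CRO representative within 24 hours whatever its causality, and has SAEs reported to the local ethics committee. It also gives the sponsor a separate 15-day duty for other information that may change the benefit-risk assessment. What is missing is a stated rule on whether such an event starts the 7- or 15-day SUAR clock.
- *The criterion under Yes that allows a clinical condition or other treatment as cause argues against relatedness.* It is compatible with *possible*, which also allows another cause.

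**Conclusion.** The point holds in limited form. The coding rule in Protocol 8.3 contradicts itself for doubtful events, and SAP section 10 carries over the conflicting definitions. Conditional and unclassifiable events are counted as *Yes* without meeting the adverse-reaction threshold. In each arm Table 22 overstates related events by the total in these three grades and disagrees with Table 25 by the same number; the R/UR tables have no cut-off.

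This assumes that sites follow the nesting as written and that Table 25 follows the stated adverse-reaction definition. The size is unknown and could be zero. A reader might infer that all the related-event tables, or the safety conclusion itself, will be wrong; the documents do not support that, because Table 23, Table 25 and the all-AE comparisons do not depend on the *Yes*/*No* answer. The primary analysis, sample size and significance level are not touched.

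**What to change.** Amend Protocol 8.3 and SAP section 10 together, before unblinding:

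1. Stop nesting *doubtful* under *Yes*, and change the definition of *No* to match.
2. Define related as definite, probable or possible, and not related as doubtful or none. Use this mapping for *Yes* in Table 22, R in Tables 29, 30, 34 and 35, and adverse reaction in Table 25. Define R and UR in the SAP.
3. Show events still conditional or unclassifiable at database lock separately from related and unrelated ones, with a sensitivity count that treats them as related. Folding them into the related category throughout would contradict the adverse-reaction definition.
4. Reconcile the causality and adverse-reaction text of 8.3 with the sponsor's reporting duties in 8.3.2, so that the protocol states how a serious unexpected event with pending causality is handled for SUAR reporting. The choice of rule is the sponsor's.

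The cost is a wording change in both documents, a small eCRF rule and one extra table row.

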Doubtful. Clinical manifestations of AEs, changes in laboratory parameters occur in the absence of a clear temporal relationship with the use of the drug; there are other factors (drugs, diseases, chemicals) that may be the cause of their occurrence.

Conditional. Clinical manifestations of an AE, abnormalities of laboratory parameters attributed to an AE are difficult to assess. Additional data is needed for evaluation, or the data is currently being analysed.

Unclassifiable. Reports of suspected AE cannot be evaluated because there is insufficient information or it is contradictory.

Foreseeability: assessed only for AEs considered to be an adverse reaction. An unexpected adverse reaction is an adverse reaction, the nature, severity or outcome of which does not correspond to the information in the current instructions for medical use of the medicinal product or in the investigator's leaflet for an unregistered medicinal product.

Version 1.0 of 12.11.2021

*Protocol-Specific Version for Protocol #PHS-
APIS-004-MEX-SOL-TAV. version 1.3 dated
07.06.2021*

CONFIDENTIAL

page 32 of 58

Plan for statistical analysis of efficacy and safety parameters

The outcome of an AE is assessed as follows:

- Transition to SAE - AE resulted in a condition that meets the criteria of seriousness (resulted in death, was life-threatening, required hospitalization of the patient or its prolongation, resulted in permanent or pronounced disability or incapacity, congenital anomalies or malformations, required medical intervention to prevent the development of these conditions. In case of any unexpected suspected transmission of an infectious agent through a medicinal product has occurred);
 - Stabilization of the condition (unchanged condition) - the AE has not resolved;
 - Recovery with consequences - resolution of an AE has occurred, but the patient still has some residual effects;
 - Recovery / cessation of an AE without consequences - AE has completely resolved with no observable residual effects;
 - Improvement of the condition is a reduction in the severity of an AE;
 - Unknown - the outcome of an AE is unknown because the patient did not show up for the follow-up examination and attempts to obtain follow-up information were unsuccessful (lost for follow-up).

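### The adverse event outcome scale has no fatal category and uses 'Transition to SAE' as an outcome, so SAP Table 28 cannot separate deaths or show how some serious events ended

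*Protocol*

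**What the plan says.** Protocol 8.3 (AE recording and reporting) describes each adverse event by several variables. Seriousness, severity and outcome are separate among them. The outcome list is "outcome (progression to SAE, stabilisation of condition, recovery without consequences, recovery with consequences, improvement in condition, unknown".

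The outcome table in the same section defines the first code by the seriousness criteria: "AE resulted in a condition that meets the criteria of seriousness (resulted in death, was life-threatening, required hospitalization of the patient or its prolongation". The definition goes on to disability, congenital anomaly and intervention needed to prevent such conditions. SAP section 10 carries this over: "Transition to SAE - AE resulted in a condition that meets the criteria of seriousness". SAP Table 28 has the same six rows, one column per arm, and a Pearson or Fisher test between arms.

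The severity scale does have a level for death: "severity (mild, moderate, severe, life-threatening, fatal". Grade 5 is defined as "Death associated with an adverse event". Seriousness has its own between-arm table, SAP Table 26.

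**The concern.** An outcome variable should say how an event ended. Here one of its six codes says instead that the event met a seriousness criterion, and death is one criterion among several within that code. Two things follow.

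- A table of outcomes by arm cannot show how many events ended in death.
- A serious event that later resolved can properly be given either of two codes.

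SAP section 10 promises adverse event statistics by outcome as well as by severity and action taken, and the safety conclusion rests on the statistical evaluation of all adverse events. What is at stake is whether Table 28 and its p-value can be interpreted, and whether the coded final state of non-fatal serious events is consistent across sites.

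**Working it through.** No formula in the plan applies here. The check sets the code lists side by side.

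**Inputs.** Protocol 8.3 (variable list, severity grades, outcome definitions), Protocol 8.3.2 (SAE reporting), SAP section 10, and SAP Tables 21, 26, 28, 29, 30, 34, 35 and 37.

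**Step 1: what each outcome code describes.**

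| Outcome code | What it describes | Fatal event | Non-fatal serious event |
|---|---|---|---|
| Transition to SAE | A seriousness criterion was met | Named in the definition | Fits |
| Stabilisation (no change) | Not resolved | Not named | Not barred |
| Recovery with consequences | Resolved, residual effects remain | Not named | Not barred |
| Recovery without consequences | Fully resolved | Not named | Not barred |
| Improvement | Severity has fallen | Not named | Not barred |
| Unknown | Lost to follow-up | Not named | Not barred |

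Of six codes, none is for death alone and one contains death together with other criteria. The severity scale has five grades, one of them for death alone.

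**Step 2: overlap.** The full-recovery code reads "The AE has completely resolved without observed residual events". It is not limited to non-serious events. An event that prolonged a hospital stay and then resolved meets this definition and also that of 'Transition to SAE'. Neither document says which code wins.

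**Step 3: what Table 28 can show.** Let *T* be the number of events in the 'Transition to SAE' row of one arm, *D* those that ended in death and *S* the rest. The table prints only *T* = *D* + *S*. Two arms with equal *T* can differ in *D*, and the test cannot detect that difference. Within *S*, the table does not show how many events resolved, left consequences or were continuing. Because the other five rows describe states of the event and this row describes seriousness, the test compares a mixture of two variables. One of them is already tested in Table 26.

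**Step 4: where deaths do appear.** Table 21 has a fatal row by arm with a Pearson or Fisher test. Tables 29 and 30 (all events) and Tables 34 and 35 (serious events) have a fatal column by MedDRA term, with randomization numbers. Table 37 lists severity, seriousness, date of resolution and outcome on one line per serious event.

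**Step 5: where the final state of a non-fatal serious event appears.** Severity does not give it. Table 37 gives a resolution date, which separates resolved from unresolved events but does not by itself show residual effects. Its outcome column has no code list in the template. No outcome summary restricted to serious events is planned.

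**The case against.** The strongest reply is that mortality is well covered elsewhere. Grade 5 events are counted and tested by arm in Table 21, and they can be traced to patients in four further summary tables and in the SAE listing. That stands, and it rules out several stronger readings that a reader might draw:

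- *An excess of deaths could be hidden from the safety conclusion.* The documents do not support this. Hiding it would require ignoring Table 21 and the fatal columns of Tables 29, 30, 34 and 35. The limitation belongs to Table 28.
- *Deaths cannot be told apart in the SAE listing.* Table 37 prints severity beside outcome, so a grade 5 event is visible on its own line.
- *Every serious event loses its final outcome.* The other five codes are open to serious events. 'Transition to SAE' could also be read as closing a non-serious event that became serious, after which Protocol 8.3.2 requires SAE reports that give the outcome to date and a further report once the event ends.
- *A fatal event that was serious from onset has no code, or Table 28 would contradict Table 21.* The definition names death, so there is a code. It is coarse and consistent with grade 5.

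The eCRF code list is also not among the documents and may already differ from the protocol's list.

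The reply leaves two things unanswered. As written, Table 28 cannot be read as a table of final outcomes. And neither severity nor seriousness says whether a non-fatal serious event resolved with or without consequences.

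**Conclusion.** The point holds as a defect of the outcome variable and of Table 28. The scale has no fatal state and mixes seriousness with final state, and its codes overlap without a precedence rule. Table 28 and its test therefore cannot isolate deaths or show the final state of events coded 'Transition to SAE', and the outcome of some non-fatal serious events may be ambiguous.

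It is minor. Mortality information is kept through severity grade 5, and no efficacy analysis is affected. No number of affected events can be derived. The documents give no expected death or SAE rate for this trial, and the only figures are from EPICA: 4 SAEs and no deaths, with 150 patients in the safety analysis. EPICA enrolled NIHSS 5 to 20 and this trial enrols 9 to 15, so those figures do not settle the rate here. How often the ambiguity arises also depends on how sites apply the overlapping codes. The conclusion assumes that the codes are applied as the protocol and SAP define them.

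**What to change.** In Protocol 8.3, SAP section 10 and SAP Table 28, replace 'Transition to SAE' with 'Fatal'. State that the outcome codes are mutually exclusive final states and that each event takes exactly one: fatal, not resolved, recovered with consequences, recovered without consequences, improved, or unknown. Report seriousness only through its own variable, in Table 26. Use the same codes in the outcome column of Table 37, and check that every grade 5 event is coded 'Fatal'.

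If the eCRF code list matches the protocol's present list, change it in the same way. Recode any events already entered under 'Transition to SAE' from the SAE reports, blinded to arm and before the database is closed. The cost is one code-list change, small edits to the protocol, SAP and templates, and that recoding. No visit or procedure changes.
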